6.3. Definition of Dose Limiting Toxicity (DLT)

Dose-limiting toxicities (DLTs) will be evaluated from the first day of administration of durvalumab (cohort 1) or durvalumab+tremelimumab (cohort 2), in this trial. The period for evaluating DLTs will be from the day of first administration of study therapy until 30 days after surgical resection or 100 days following the last dose of study therapy, whichever occurs later. Subjects who do not remain on the study up to this time for reasons other than DLT will be replaced with another subject. Grading of DLTs will follow the guidelines provided in the Common Terminology Criteria for Adverse Events (CTCAE) version 4.0. A patient who experiences a DLT will be permanently discontinued from treatment and will proceed to surgery after standard preoperative evaluation by a surgeon and anesthesiologist. Prior to surgery any treatment related toxicity should have resolved to ≤grade 1. [5]

A DLT will be defined as any Grade 3 or higher toxicity that occurs during the DLT evaluation period. Toxicity that is clearly and directly related to the primary disease or to another etiology is excluded from this definition. The following will be DLTs:

- Any Grade 4 irAE
- Any ≥ Grade 3 colitis
- Any Grade 3 or 4 non-infectious pneumonitis irrespective of duration
- Any Grade 2 pneumonitis that does not resolve to ≤ Grade 1 within 3 days of the initiation of maximal supportive care
- Any Grade 3 irAE, excluding colitis or pneumonitis, that does not downgrade to Grade 2 within 3
 days after onset of the event despite optimal medical management including systemic
 corticosteroids or does not downgrade to ≤ Grade 1 or baseline within 14 days
- Liver transaminase elevation > 8 × ULN or total bilirubin > 5 × ULN
- Any ≥ Grade 3 non-irAE, except for the exclusions listed below

The definition excludes the following conditions:

- Grade 3 fatigue lasting ≤ 7 days
- Grade 3 endocrine disorder (thyroid, pituitary, and/or adrenal insufficiency) that is managed
 with or without systemic corticosteroid therapy and/or hormone replacement therapy and the
 subject is asymptomatic
- Grade 3 inflammatory reaction attributed to a local antitumor response (e.g., inflammatory reaction at sites of metastatic disease, lymph nodes, etc.)
- Concurrent vitiligo or alopecia of any AE grade
- Grade 3 infusion-related reaction (first occurrence and in the absence of steroid prophylaxis) that resolves within 6 hours with appropriate clinical management

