12.2.2. Safety Endpoint

Safety stopping rule:

To minimize the risks of adding durvalumab monotherapy (cohort 1) or durvalumab+tremelimumab (cohort 2) to thoracic radiation prior to surgery, safety will be monitored by a Bayesian stopping rule for the rate of adverse events of interest (Section 9.2). Previous experience with single and multiple dose schedules of durvalumab and durvalumab+tremelimumab demonstrated that the incidence of grade 3-4 toxicities in advanced NSCLC and other solid tumors is low. The primary DLTs of concern for safety monitoring will be grade 3-4 toxicities of the types listed in section 6.3. These include liver, GI, renal, pneumonitis and any other grade 3-4 toxicity that in the opinion of the investigator significantly interfered with the subjects' optimal perioperative management. They will be monitored continuously for sixteen patients through day 90 following the last dose of immunotherapy (or day 30 post-surgery, whichever is longer).

AEs will be monitored continuously for all patients. A Bayesian safety monitoring rule will be used to evaluate the rate of the AE of interest continuously, from the 3rd evaluable patient, and will suspend accrual at any point if there is sufficient evidence of excessive toxicity. Specifically, the Bayesian toxicity monitoring rule will suspend accrual anytime if the posterior probability of AE of interest being larger than 25%, is 70% or higher. We assume a priori that the experimental regimens has an average risk around 5% and there is about 7% chance that the risk will be 25% or higher. This corresponds to a Beta (0.05,0.95) prior distribution. Table 10.1 summarizes the continuous stopping rule for the 16 evaluable patients for each regimen. For example, if 2 patients out of the first 3 or 4 evaluable patients experience adverse events of interest, we will stop accrual. Furthermore, to cautiously assess the toxicity profiles of experimental regimens in the event that accrual is relatively "fast" comparing to the safety assessment duration, the accruals of each cohort will be suspended when 6 eligible patients have been accrued to allow the continuous safety evaluations to be done among the first 6 evaluable patients before further accruals. The accrual would resume only if the following Bayesian stopping rule being used is not met. At any time if the stopping criterion is met, accrual to the trial will be temporarily suspended and the

18-Nov-2020 Page **115** of **164**

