principle investigators and study team will review the toxicity data and recommend either modification or termination of the trial.

TABLE 10.1 STOPPING RULE FOR SAFETY

# patients with DLT	2	3	4	6
Out of total # patients treated	3-4	5-7	8-11	16

Table 10.2 summarizes the operating characteristics based on 5,000 simulations with 16 evaluable patients in terms of how frequent the study would stop based on the stopping rule under different hypothetical toxicity rates, as well as the average sample sizes.

TABLE 10.2 OPERATING CHARACTERISTICS OF THE STOPPING RULE FOR SAFETY

Underlying risk	0.15	0.20	0.25	0.30	0.35
% of time study stops	15.8%	29.3%	43.1%	60%	72.8%
Expected sample size	14.3	13	11.7	10	8.6

Early Stopping Plan for Treatment-related Grade 5 AE

We will also evaluate the rate of treatment-related grade 5 AE if it's convincingly greater than 10%. Specifically, the Bayesian toxicity monitoring rule that suspends the accrual anytime if the posterior probability of treatment-related grade 5 AE being larger than 10% is 70% or higher. We assume a priori that the experimental regimens has an average risk 5% and there is about 14% chance that the risk will be 10% or higher. This corresponds to a Beta (0.1,1.9) prior distribution. Table 10.3 summarizes the continuous stopping rule for the 16 evaluable patients for each regimen.

TABLE 10.3 EARLY STOPPING RULE FOR GRADE 5 ADVERSE EVENT

# patients with grade 5 AE	1	2	3
Out of total # evaluable patients	1-3	4-10	11-16

Table 10.4 summarizes the operating characteristics based on 5,000 simulations with 16 evaluable patients in terms of how frequent the study would stop based on the stopping rule under different hypothetical grade 5 AE rates, as well as the average sample sizes.

18-Nov-2020 Page **116** of **164**

TABLE 10.4 OPERATING CHARACTERISTICS OF THE STOPPING RULE FOR GRADE 5 AE

Underlying risk	0.04	0.08	0.10	0.12	0.16	0.20
% of time study stops	6.4%	21.5%	32.2%	38.8%	57.5%	72.4%
Expected sample size	15.5	14.4	13.6	13.1	11.6	10.4

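### Table 10.2 understates expected enrolment at stopping, because it fits only a model with instant DLT outcomes; the rule's denominator is also labelled two ways

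*Combined protocol and SAP*

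**What the plan says.** Section 12.2.2 will "suspend accrual anytime if the posterior probability of AE of interest being larger than 25%, is 70% or higher". On the prior it says: "This corresponds to a Beta (0.05,0.95) prior distribution". The rule is applied "continuously, from the 3rd evaluable patient, and will suspend accrual at any point if there is sufficient evidence of excessive toxicity". The section recognises that accrual may outpace safety assessment and adds one pause: "the accruals of each cohort will be suspended when 6 eligible patients have been accrued". No later pause is planned unless a boundary is met.

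The basis of the operating characteristics is given only as follows: "Table 10.2 summarizes the operating characteristics based on 5,000 simulations with 16 evaluable patients". No accrual rate, DLT timing or pause is mentioned.

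The DLT window in Section 6.3 runs "until 30 days after surgical resection or 100 days following the last dose of study therapy, whichever occurs later". Section 12.2.2 has a shorter one: "They will be monitored continuously for sixteen patients through day 90 following the last dose of immunotherapy", or 30 days after surgery if that is later. Doses fall on days 1, 30 and 60 (Section 6.2.1). Accrual is 1–2 per month (Section 12.5).

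Section 12.1 requires complete toxicity follow-up for a patient to be evaluable, and the text of 12.2.2 counts evaluable patients. The row label in Table 10.1 reads "Out of total # patients treated".

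**The concern.** A rule that looks after every patient limits exposure only as fast as outcomes arrive. Here a patient's outcome can take five months to settle, and patients may enter every two to four weeks. Figures computed as if outcomes were instant will then show fewer patients exposed to a toxic regimen than the trial would actually expose. The expected sample size in Table 10.2 is what a safety committee would read as that exposure.

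The two denominators matter for the same reason. With instant outcomes, treated and evaluable patients are the same count. With delayed outcomes they are not, and the same boundary behaves differently under each.

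**Working it through.** **1. Boundary.** After r DLTs in n patients the posterior is Beta(0.05 + r, 0.95 + n − r). The rule stops when Pr(rate > 0.25) ≥ 0.70. This gives 2 DLTs at n = 3–4, 3 at 5–7, 4 at 8–11, 5 at 12–14 and 6 at 15–16. Table 10.1 as available shows no entry for n = 12–15, so those values come from the stated prior and cut-off.

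**2. Reproducing Table 10.2.** An exact binomial recursion was run patient by patient from n = 3 to 16, with each outcome known before the next entry and no pause.

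| True risk | 0.15 | 0.20 | 0.25 | 0.30 | 0.35 |
|---|---|---|---|---|---|
| Stated stop | 15.8% | 29.3% | 43.1% | 60% | 72.8% |
| Recomputed stop | 16.3% | 29.3% | 44.3% | 59.4% | 72.8% |
| Stated N | 14.3 | 13 | 11.7 | 10 | 8.6 |
| Recomputed N | 14.26 | 13.00 | 11.54 | 10.04 | 8.59 |

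Every cell agrees within 1.2 points and 0.2 patients.

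**3. Timing.** Day 60 + 100 = day 160 (Section 6.3); day 60 + 90 = day 150 (Section 12.2.2). Surgery plus 30 days falls earlier, at about day 105–135. With evenly spaced entry:
- At 2 per month (15.2 days apart), patient 6 enters 5 × 15.2 = 76 days after patient 1, and patient 16 enters 9 × 15.2 = 137 days after patient 7. All of patients 7–16 are therefore in before patient 7 completes either window.
- At 1 per month (30.4 days apart), patient 6 enters on day 152. Of patients 7–16, 6 have entered before patient 7 completes a 160-day window (5 with 150 days).
- With the 160-day window, none of the first six has completed follow-up when patient 6 enters.

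**4. Part of the gap by hand.** The instant model stops at n = 3 with probability 0.156 and at n = 4 with probability 0.105 when risk is 25%; at 35% these are 0.282 and 0.155. If outcomes count at completion, six patients are already enrolled in those trials. That alone adds 0.156 × 3 + 0.105 × 2 = 0.68 patients at 25% and 0.282 × 3 + 0.155 × 2 = 1.16 at 35%.

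**5. Simulation with staggered entry.** Settings: Poisson accrual, 160-day window, pause after patient 6 until all six outcomes are known. Ranges run from 1 to 2 patients per month. DLT onset is uniform over the window (an assumption), except in the completed follow-up row, where onset has no effect. Cells show chance of crossing / accrual halted before patient 16 / expected number enrolled.

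| Who counts | Risk 25% | Risk 35% |
|---|---|---|
| Table 10.2 | 43.1% / not given / 11.7 | 72.8% / not given / 8.6 |
| Instant outcomes | 44.3% / 43.7% / 11.5 | 72.8% / 71.6% / 8.6 |
| Completed follow-up | 45–44% / 37–30% / 12.8–13.1 | 73% / 62–51% / 10.7–11.1 |
| Entry order, outcome known | 45% / 40–34% / 12.6–12.9 | 73% / 64–55% / 10.4–10.9 |
| All treated | 32–28% / 28–21% / 13.5–14.0 | 63–60% / 55–43% / 11.1–12.0 |
| DLT at once, DLT-free at completion | 56–60% / 52–49% / 11.5 | 82–85% / 76–72% / 9.1–9.3 |

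Taking repeat runs of the completed follow-up and entry-order readings together, halting before patient 16 is about 31–39% at 25% risk and 53–64% at 35%; the cells above lie within about 2.5 points of that. Repeat runs of the last two rows at 25% risk span 28–33% and 53–62%. A 150-day window changes little: entry order gives 12.6–12.9 enrolled at 25% and 10.3–10.7 at 35%.

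Over all three ways of counting simulated with varying onset (entry order, all treated, DLT at once) and all onset patterns tried (first half, uniform, second half, end of window), crossing ranges over 26–66% at 25% risk and 58–87% at 35%. Enrolment ranges over 11.0–14.3 and 8.5–12.5.

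**The case against.** The strongest reply is that Section 12.1 defines evaluable patients by complete toxicity follow-up, and that the text of 12.2.2 and the title of Table 10.2's simulation both use that term. On that definition the chance of crossing the boundary is preserved. This stands. A reader might infer that the stated stopping rates are not delivered, or that the rule is much weaker than claimed. The documents do not support that: it follows only if the row label of Table 10.1 overrides the text. What the reply does not rescue is the expected sample size, since patients keep entering while outcomes are pending.

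A second reply is that the plan foresaw the problem. The pause at 6 does help: without it, at 2 per month in entry order, expected enrolment would be 15.0 at 25% risk and 14.2 at 35%. Weekly investigator meetings, weekly record review and six-monthly board review also apply, and crossing the boundary triggers suspension and review, not automatic closure. All this limits the harm. But every staggered-entry figure in the table above already includes the pause, and the gap remains.

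Third, the documents give no DLT onset pattern, so the exact size is not fixed. That is fair. It is also a reason to state the pattern assumed in the simulation.

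**Conclusion.** The point holds in a limited form. Under the protocol's own definition of evaluable, or in entry order, the stopping probabilities of Table 10.2 survive, but its expected sample sizes are too low. They are low by about 1 to 1.4 patients at 25% risk (12.6–13.1 against 11.7) and by about 1.8 to 2.5 at 35% (10.4–11.1 against 8.6). Accrual is also halted before the cohort fills less often than the table's model implies.

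Separately, the unreconciled labels leave stopping at 25% risk anywhere from about 28–33% (all treated) to 53–62% (DLTs at once, others at completion), in opposite directions from the stated 43.1%.

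The assumptions are 1–2 patients per month, a window to day 150–160, one pause at patient 6 and DLT onset uniform over the window. The instant-outcome basis of Table 10.2 is inferred from the close match; the plan does not state it. The claim that all of patients 7–16 enter before patient 7 completes holds at 2 per month, not at 1.

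**What to change.** - In Section 12.2.2 and Table 10.1, use one denominator: evaluable patients with complete follow-up, taken in entry order. State how patients still inside the window are handled.
- Reconcile the 90-day window of Section 12.2.2 with the 100-day window of Section 6.3. Sections 10.1.1 and 14.2, which end monitoring at the earlier of the two dates, need the same attention.
- Re-simulate Table 10.2 with 1–2 patients per month, the pause at 6 and a stated range of DLT onset patterns. Report the chance of crossing, the expected number enrolled at stopping, and the chance that accrual is halted before patient 16.

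Time-weighted counting of patients in follow-up is optional. Linear weights suit DLTs spread evenly over the window; with onset confined to days 0–60 (an assumption), such a rule stopped 22–23%, 52–54% and 78–81% of trials at 15%, 25% and 35% risk. Table 10.6 should not be re-run with the 160-day window, because feasibility is judged at 8 weeks after radiation ends.

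The cost is one paragraph and a re-simulation. The stated expected sample sizes become about 1–2.5 patients less favourable at 25–35% risk.

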3.1.6.2. Evaluation of Perioperative Safety

The subject's medical record will be reviewed on a weekly basis from the start of therapy until 100 days after the last dose of study therapy or 30 days following surgery, whichever occurs later. The medical record will be reviews for information regarding operative complications including delay in planned surgery and in particular potential immune related toxicities (Note: Only those subjects who initiate study therapy will be followed). Toxicities will be reviewed at regular meetings of study investigators and minutes of these meetings will be documented by the clinical research staff. In the event that a subject does not continue his or her peri-operative care at the institution, every attempt will be made to collect this information either by direct contact or through communication with the subjects outside physician(s).

[figure not shown]
Deaths that occur during the DLT period will be assessed for their relationship to study therapy. As per section 1.6.5, historical norms for perioperative mortality with preoperative chemoradiation are in the order of 4%. If there is an early death in the study that is deemed related to study therapy such that the perioperative mortality rate exceeds that of historical norms, the study will be closed. If an early death occurs that is not deemed to be related to study therapy, the study may be allowed to continue in conjunction with safety assessments outlined in section 9.0.

FIGURE 2: STUDY SCHEMA

Cohort 2 opens when safety and feasibility of cohort 1 established

18 Nov 2020 Page **58** of **164**

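### Table 10.4 does not describe the grade 5 stopping rule in Table 10.3, which stops more often and earlier than stated and is not reconciled with the death rule in Section 3.1.6.2

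*Combined protocol and SAP*

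**What the plan says.** Under the grade 5 plan in Section 12.2.2, accrual is suspended at any time if "the posterior probability of treatment-related grade 5 AE being larger than 10% is 70% or higher". The prior is Beta(0.1, 1.9), described as a mean risk of 5% with about a 14% chance of a risk of 10% or more. "Table 10.3 summarizes the continuous stopping rule for the 16 evaluable patients for each regimen": 1 event in 1-3 patients, 2 in 4-10, 3 in 11-16. Table 10.4 is then given as the operating characteristics of that rule: "Table 10.4 summarizes the operating characteristics based on 5,000 simulations with 16 evaluable patients in terms of how frequent the study would stop".

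The text names no first look for grade 5. The DLT rule in the same section runs "continuously, from the 3rd evaluable patient, and will suspend accrual at any point", and the feasibility rule in Section 12.2.3 starts at the 6th evaluable patient. Section 12.2.2 also says that "the accruals of each cohort will be suspended when 6 eligible patients have been accrued", but that hold is written for the DLT rule.

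Section 3.1.6.2 has a second death provision. It states that "historical norms for perioperative mortality with preoperative chemoradiation are in the order of 4" per cent, and that if an early death is judged related to study therapy "such that the perioperative mortality rate exceeds that of historical norms, the study will be closed". The note to Figure 2 adds: "Cohort 2 opens when safety and feasibility of cohort 1 established".

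**The concern.** Table 10.3 stops on any related death among the first three patients. At a true rate of 4%, that column alone is reached with probability 1 − 0.96³ = 11.5%. Table 10.4 gives 6.4% for the whole 16-patient rule, which cannot be right for the printed boundary.

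Table 10.4 is what an IRB or monitoring committee would use to judge how readily the rule halts accrual when the regimen is acceptable, and how reliably it does so when it is not. If the table belongs to a different rule, they are judging the wrong one. There is also a practical question after a first related death: one section can close the study, while the other may call for no action.

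**Working it through.** **Inputs (Section 12.2.2).** Prior Beta(0.1, 1.9); stop if P(rate > 0.10 | data) ≥ 0.70; at most 16 evaluable patients; 5,000 simulations.

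**Step 1: reproduce the boundary.** After k events in n patients the posterior is Beta(0.1 + k, 1.9 + n − k). The posterior probabilities of a rate above 10% at the change points are:

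- 1 event: 0.850 (n=1), 0.775 (n=2), 0.705 (n=3), 0.641 (n=4)
- 2 events: 0.727 (n=10), 0.690 (n=11)
- 3 events: 0.783 (n=16)

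This gives 1 in 1-3, 2 in 4-10 and 3 in 11-16, exactly Table 10.3. The prior probability of a rate above 10% is 13.9%, matching the stated 14%.

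**Step 2: check the method on the DLT rule.** An exact recursion over the number of events, with a look after every patient, was applied to the Beta(0.05, 0.95) DLT rule from patient 3. At risks of 0.15/0.20/0.25/0.30/0.35 it gives 16.3/29.3/44.3/59.4/72.8%, with expected sizes 14.3/13.0/11.5/10.0/8.6. Table 10.2 states 15.8/29.3/43.1/60/72.8% and 14.3/13/11.7/10/8.6. The method agrees with the plan's own DLT table.

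**Step 3: apply it to Table 10.3, looks from patient 1.**

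| True rate | Stop %, Table 10.4 | Stop %, printed rule | Gap (points) | z, 5,000 runs | E[N], Table 10.4 | E[N], printed rule |
|---|---|---|---|---|---|---|
| 0.04 | 6.4 | 14.6 | 8.2 | −16.5 | 15.5 | 14.2 |
| 0.08 | 21.5 | 32.5 | 11.0 | −16.7 | 14.4 | 12.2 |
| 0.10 | 32.2 | 41.7 | 9.5 | −13.6 | 13.6 | 11.3 |
| 0.12 | 38.8 | 50.4 | 11.6 | −16.4 | 13.1 | 10.4 |
| 0.16 | 57.5 | 65.9 | 8.4 | −12.6 | 11.6 | 8.7 |
| 0.20 | 72.4 | 78.0 | 5.6 | −9.6 | 10.4 | 7.2 |

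Here z = (stated − exact)/√(p(1 − p)/5000), with p the exact stopping probability. A separate run of 200,000 simulated trials gives 14.7/32.6/41.7/50.6/65.7/78.0%.

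**Step 4: does a later start explain it?**

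- First look at patient 3, as in the DLT rule: the stopping probabilities do not change, because a death in patients 1-2 still meets the boundary at patient 3. E[N] is 14.3/12.5/11.6/10.7/9.1/7.8, still well below Table 10.4.
- First look anywhere from patient 4 to 7, so that the one-death column never applies: 6.5/22.1/31.4/40.8/58.4/72.7%. Five columns are within 1.3 standard errors of Table 10.4; the 0.12 column is 2.9 away.
- E[N] fits a first look near patient 6 (15.5/14.4/13.7/13.0/11.5/10.3) better than one at patient 4 (9.8 at rate 0.20, against 10.4 stated).

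Table 10.4 is therefore consistent with a simulation that left out the one-death stop. The documents do not say so, and the fit does not prove it.

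**Step 5: the two death provisions.** One death is 1/16 = 6.25%, 1/20 = 5%, 1/24 = 4.17%, 1/25 = 4.0% and 1/32 = 3.1%. It exceeds 4% at any denominator below 25. Cohort 1 plans 20 patients (Section 12.1) and cohort 2 follows it, so during cohort 1 a single related death is at least 5% of those treated so far. Under Table 10.3 a first related death at patient 4 or later does not suspend accrual, nor does a second at patient 11 or later. The actions also differ: closure in Section 3.1.6.2, suspension of accrual in Section 12.2.2.

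**Minor: DLT boundary.** The 70% DLT criterion gives 5 of 12-14 (posterior 0.850, 0.802, 0.751) and 6 of 15-16 (5 of 15 gives 0.696; 6 of 15 gives 0.858). Table 10.1 shows nothing for patients 12-15, and the synopsis table nothing for 14-15. At 30% risk the stopping probability is 59.4% for the complete rule, 57.7% for Table 10.1 as shown and 58.2% for the synopsis version.

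**The case against.** The table mismatch is not open to serious dispute. The objections concern its reach.

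- **Not all of the gap is false stopping.** Only 0.04 and 0.08 lie below the 10% limit. At 0.12 and above stopping is the intended result, so there Table 10.4 understates correct stopping. Stopping also means suspension and review, not automatic termination. Both points stand: false stopping is understated by 8.2 and 11.0 points, and the 11.6-point maximum is in a column where stopping is wanted.
- **The start is implied.** The text allows suspension at any time and Table 10.3 begins at patient 1. That is the natural reading. But Table 10.4 fits a later start, and the text gives a first look for the other two rules and none for this one, so the sponsor still has to say which was meant.
- **The two death provisions can coexist.** One concerns perioperative mortality against a historical norm, the other any treatment-related grade 5 event, and the stricter could simply apply. Not meeting Table 10.3 does not override another section. Pooled over 32 patients, one death is only 3.1%. Replacement of treated subjects, or an amendment, could also take cohort 1 beyond 20. All of this is fair, but a related perioperative death falls under both provisions, neither refers to the other, and the missing denominator decides whether the study closes. Cohort 1 would need 25 treated patients before one death fell to 4%.
- **The Table 10.1 gap may come from text extraction** and costs under 2 points. It is kept only as a minor item.

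**Conclusion.** The concern holds. Table 10.4 is wrong for the rule in Table 10.3: the stopping probability is understated by 5.6 to 11.6 points and the expected sample size overstated by 1.3 to 3.2 patients. At 4%, the plan's own historical mortality figure, the chance of a stop is more than twice what is stated (14.6% against 6.4%). This assumes a look after every evaluable patient from patient 1, independent outcomes and a constant rate; starting at patient 2 or 3 leaves the stopping probabilities unchanged. Why the table differs is not established.

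Because Table 10.3 is correct for its prior, applying it as printed costs patients no protection. The harm is that reviewers see a rule that looks less likely to stop than it is. The lack of reconciliation with Section 3.1.6.2 is also real, though how far the two conflict depends on a denominator the plan does not give. This should be fixed.

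**What to change.** 1. Confirm when grade 5 looks begin. If at patient 1, as Table 10.3 implies, replace the Table 10.4 stopping rates with 14.6/32.5/41.7/50.4/65.9/78.0% and the expected sizes with 14.2/12.2/11.3/10.4/8.7/7.2. If later, state the starting patient in Section 12.2.2 and in Table 10.3, and rerun Table 10.4 for that rule.
2. Reconcile Section 3.1.6.2 with Table 10.3. State the denominator (per cohort or pooled; treated or operated) and which action follows, cross-refer the two sections, and give the operating characteristics of whatever rule is kept. Which provision governs is for the sponsor and investigators to decide.
3. Minor: complete Table 10.1 and the synopsis table to match the 70% criterion (5 of 12-14, 6 of 15-16).

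The cost is low: one clarification, one recomputed table and one cross-reference. If looks do begin at patient 1, the disclosed false-stop rate rises.
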